#### Appendix 1: Schedule of Activities

		Optional Ocrelizumab Extension (264 Weeks) a																it d	d, e		0		
Site or optional MN visit b	10 (MN)	11 (MN)	12	13 (MN)	14 (MN)	15	16 (MN)	17 (MN)	18	19 (MN)	20 (MN)	21	22 (MN)	23 (MN)	24	25 (MN)	26 (MN)	27	28 (MN)	sing Vis	for SD	ite/MN 	tmt Visit
Week	36	46 c	48	60	70 c	72	84	94 c	96	108	118 c	120	132	142 c	144	156	166 c	168	180	ß	/isit	d. Si	Ē
Study day (±days)	253 (±6)	323 (±6)	337 (±6)	421 (±6)	491 (±6)	505 (±6)	589 (±6)	659 (±6)	673 (±6)	757 (±6)	827 (±6)	841 (±6)	925 (±6)	995 (±6)	1009 (±6)	1093 (±6)	1163 (±6)	1177 (±6)	1261 (±6)	Delayed	Opt Inf \	Unsched	WD fron
PK samples (predose and postdose) cc			x			x			x											(x)			(x)
ADA dd			х			х			х											(X)			(X)
Pre-medications ee			х			х			х			х			х			х		x	х		
Ocrelizumab administration c, e, h			x			x			x			x			x			x		x	x		

#### Table 2a Schedule of Activities for Optional Ocrelizumab Extension Period (Weeks 36 to 180) (cont.)

ADA = anti-drug antibody; AE = adverse event;  $\beta$ -hCG = beta-human chorionic growth hormone; EC = Ethics Committee; eCRF = electronic case report form; EDSS = Expanded Disability Status Scale; ETDRS = Early Treatment Diabetic Retinopathy Study; Gd = gadolinium; HbcAb = hepatitis B core antigen; HbsAg = hepatitis B surface antigen; HBV = hepatitis B virus; HepCAb = hepatitis C antibody; Ig = immunoglobulin; IMC = Internal Monitoring Committee; Inf. = infusion; IRB = Institutional Review Board; IRR = infusion-related reaction; JCV = JC-virus; LCVA = low-contrast visual acuity; LLN = lower limit of normal; MN = mobile nursing; MRI = magnetic resonance imaging; OOE = Optional Ocrelizumab Extension; opt = optional; PA = posteroanterior; PCR = polymerase chain reaction; PK = pharmacokinetic; SAE = serious adverse event; SD = split dose; SDMT = Symbol Digit Modalities Test; SFU = safety follow-up period; Trtmt = treatment; Unsched = unscheduled; WD = withdrawal; wk(s) = week(s).

Notes:

Marks in parentheses are optional and may be done as appropriate (e.g., if not done at the scheduled dosing visit or if needs to be repeated).

Columns shaded in gray indicate visits that include an ocrelizumab infusion.

(MN) indicates that this visit may be performed as a mobile nursing visit. Note for the screening visit: For the patient's convenience, the mobile nursing service can be requested if any laboratory tests have to be repeated.

For consistency, it is recommended the same examiner will perform the same assessment at each visit using the same instrument in the same patient.

a In this study, patients will be offered the possibility to continue ocrelizumab treatment in an optional treatment extension period with the dose

(e.g., 300 mg or 600 mg) initially assigned to them until the appropriate dose for the subsequent Phase III study in children/adolescents is selected by the IMC

Ocrelizumab—F. Hoffmann-La Roche Ltd 136/Protocol WA39085, Version 10

(see Section 3.1.1.3). At that time, patients will be assigned to this selected dose level. In a situation where a subsequent dose of ocrelizumab is higher than the initial dose, that dose must be administered as two infusions of half the dose 14 days apart to mitigate the risk and severity of IRRs. In this case, the second infusion will take place as an optional infusion visit for split dose. For patients continuing the study, the second dose of ocrelizumab will be administered if all re-treatment criteria are met (footnote c). It is recommended that the treating investigator discuss with the parents/legal guardian and patient the benefits and risks of continuing study treatment with ocrelizumab, including treatment options, in advance and prior to any further dosing in order to schedule subsequent visits. The OOE period will last 264 weeks, and may be extended until the patient turns 18 years old (or as required per local regulation) or until commercial ocrelizumab is approved for children and available in the country for these patients, whichever occurs first. Initiation of an alternative treatment for MS may be considered by the investigator in which case the patient will enter the SFU period.

- b **Optional MN visits**: At applicable sites, for patient convenience, all assessments at visits marked with (MN) may be performed by an MN professional at the patient's home or another suitable location instead of the clinical site (see Section 4.5.3.5). If during a visit the MN professional identifies any change in patient's health status (e.g., new or worsening neurologic symptoms or any other situation that may warrant an unscheduled site visit), the MN professional will contact the site immediately to report and discuss the findings. If required, an unscheduled visit will be scheduled as soon as possible with the site (i.e., within 7 days of symptom onset if possible). At sites where MN visits are not applicable, visits will take place at the clinical site.
- c Prior to re-treatment with ocrelizumab, patients must be evaluated for the conditions and laboratory abnormalities described in Section 4.3.6 of the protocol. If any of these conditions are present prior to re-dosing, further administration of ocrelizumab should be suspended until resolved or held indefinitely. A site visit or optional MN visit (as applicable) within 2 weeks prior to a planned or delayed dosing visit will be required to collect blood samples and patient's information to enable the treating investigator to assess whether a patient meets re-treatment criteria at the time of an infusion with ocrelizumab. Treating investigator must have reviewed all safety laboratory data and ensure that any repeat laboratory tests have been performed, analyzed, and reviewed before administration of ocrelizumab. If these conditions are not met, an unscheduled visit and/or delayed dosing visit must occur.
- d A delayed dosing visit will be performed and recorded in the Delayed Dosing Visit eCRF form when dosing cannot be administered at the scheduled dosing visit. Other tests or assessments may be done as appropriate. A site visit or optional MN visit (as applicable) within 2 weeks prior to a delayed dosing visit will be required to collect blood samples and patient's information to enable the treating investigator to assess whether a patient meets criteria for re-treatment with ocrelizumab (footnote c). Note that in situations where the delayed dosing visit occurs more than 4 weeks after the planned infusion date, the dose should be administered as two infusions of half the dose 14 days apart. In this case, the second infusion will take place as an optional infusion visit for split dose.

e Administration of IV ocrelizumab: The first dose of ocrelizumab must be administered as two infusions of half the dose 14 days apart (e.g., 150 mg on Day 1 and 150 mg on Day 15 for the 300 mg ocrelizumab cohort). It is recommended to schedule the first infusion of ocrelizumab (Day 1 of Dose 1) in the morning to allow the patient to stay at the hospital (or infusion center) with medical supervision and monitoring as required, as long as possible (e.g., until 6 p.m. or 8 p.m. according to the hospital rules), with a minimum of 1 hour after completion of the infusion. Patients may be hospitalized for a 24-hour observation after completion of the infusion at the discretion of the treating investigator. It is also recommended to administer the second infusion (Day 15 of Dose 1) and subsequent infusions in the morning, as patients should remain under observation for at least 1 hour after the completion of the infusion and up to 24 hours at the treating investigator's discretion.

For patients continuing in the optional ocrelizumab extension period (footnote a), subsequent doses will be administered as single infusions (e.g., 300 mg for the 300-mg ocrelizumab cohort). However, whenever the subsequent dose is higher than the previous dose, it should be administered as two infusions of half the dose 14 days apart. In this case, the second infusion will take place as an optional infusion visit for split dose. Prior to subsequent infusion of ocrelizumab, the treating investigator must review the clinical and laboratory re-treatment criteria (footnote c). Patients and their parents/legal guardian will be advised that an IRR can occur until 24 hours after completion of each infusion. A telephone interview will be conducted by site personnel within 24 ( $\pm$  4) hours after completion of each infusion (footnote h).

- f Unscheduled site or MN visit: Assessments performed at unscheduled (non-dosing) visits will depend on the clinical needs of the patient. All patients with new neurological symptoms suggestive of relapse should have EDSS performed within 7 days of the onset of the relapse. Other tests/assessments may be done as appropriate.
- g Withdrawal from treatment visit only takes place if patient discontinues prematurely from treatment (i.e., before Week 288) (see Section 4.5.3.6).
- h A telephone interview will be conducted by site personnel within 24 (± 4) hours after completion of each infusion and every 4 weeks (± 6 days) between any visit (MN or site visit) and throughout the entire SFU period to identify and collect information on any changes in the patient's health status that warrant an unscheduled visit (including new or worsening neurological symptoms or signs of infection) (see Appendix 4).
- i Determination of the LCVA will include a measure of high-contrast acuity using the ETDRS chart as described in Appendix 3 of the protocol.
- j At screening and baseline, a complete physical examination will be performed and should include an evaluation of the head, eyes, ears, nose, and throat and of the cardiovascular, dermatologic, musculoskeletal, respiratory, gastrointestinal, genitourinary, and neurologic systems. At subsequent visits, a limited, symptom-directed physical examination should be performed. Any abnormality identified should be entered either as medical history or AE accordingly.
- k Body weight is to be determined to the nearest 0.1 kg. For body weight measurements, the patient should wear clothes, without any shoes, outerwear, or accessories.

-  Height should be measured in a standing position using the same wall-mounted stadiometer for the same individual. Three standing height measurements should be made. The average of the three measurements will be considered to be the true height of the child/adolescent, provided the measurements are within 0.3 cm. The average value will be recorded on the eCRF. Note: Height should be collected from consenting biological mothers and fathers. This information should be entered directly on the eCRF. If both parents are not able to attend the same visit, please collect the missing height at a next clinic visit. If the parents are unknown this assessment will not be applicable.
- m Tanner staging assessment will be contingent on IRB/EC's approval and written informed consent from the patients' parents/legal guardian and with patient assent (as applicable). Tanner staging will be documented on the eCRF at baseline. During the study conduct, patients will have their Tanner stages documented or assessed yearly until they reach Stage 5 (see Section 4.5.8).
- n Wrist/Hand X-ray: This radiographic assessment will be contingent on IRB/EC's approval and written informed consent from the patients' parents/legal guardian and with patient assent (as applicable). One combined standard PA radiograph of the left wrist and hand will be obtained within 4 weeks of baseline and repeated yearly (± 4 weeks). If evidence of growth-plate fusion is not demonstrated at baseline but during subsequent X-rays, no further hand/wrist X-rays will be necessary provided that final growth/bone maturation has unequivocally been reached (see Section 4.5.10).
- o If a prior X-ray was obtained within the last 6 months before the WD visit, the X-ray should not be repeated.
- P MRI scans will be performed without a Gd-contrast agent at Week 24, Weeks 48, 72, 96, 144, 192, 240, and 288 (window of ± 4 weeks of these scheduled visits). Also, MRI scans will be obtained in patients withdrawn from the treatment period (at a withdrawal from study visit), if not performed during the last 4 weeks.
- q Neurological examination and EDSS: See Sections 4.5.14 and 4.5.15.
- r Concomitant medications: See Section 4.4.
- s Adverse events: See Section 5.
- t Sensitive thyroid-stimulating hormone will be tested at screening and during the treatment period as indicated.
- u Hepatitis screening and monitoring: All patients must have negative HbsAg and negative HepCAb screening test results prior to enrollment. If total HbcAb is positive at screening, HBV DNA measured by PCR must be negative to be eligible. For those patients enrolled with negative hBsAg and positive total HbcAb, HBV DNA (PCR) must be repeated every 12 weeks during the treatment period.
- Immunologic assessments: Includes CD19 and other circulating B-cell subsets, T cells, and natural killer cells. On infusion visits, blood samples should be collected prior to the methylprednisolone administration.
- Routine safety laboratory (hematology, chemistry, and urinalysis): On infusion visits, all urine and blood samples should be collected prior to the methylprednisolone administration. At other times, samples will be collected at any time during the visit. For urinalysis, a urine dipstick for blood, protein, nitrite and glucose (using the dipsticks provided) will be performed. If abnormal and applicable a microscopic examination will be performed on site (local laboratory). For more information related to safety laboratory assessments, see Section 4.5.19.1.

- x Serum  $\beta$ -hCG must be performed at screening in female patients of childbearing potential (e.g., in Tanner stages  $\geq$  2 or post-onset of menarche). Subsequently, urine  $\beta$ -hCG (sensitivity of at least 25 mIU/mL) will be performed. On infusion visits, the urine pregnancy test should be performed prior to the methylprednisolone administration in all female patients of childbearing potential. If positive, the patient will not receive the scheduled dose, and confirmation by a serum pregnancy test will be performed.
- y Antibody titers: Measurement of antibody titers against common antigens (mumps, rubella, varicella zoster, and S. pneumoniae) will be performed.
- z Plasma and urine samples for JCV will be collected at specified timepoints and analyzed in batches, if decided by the Sponsor.
- aa ECG (predose and postdose): At screening, ECG may be taken at any time during the visit. On infusion visits, ECGs should be performed prior to receipt of study drug, prior to vital sign measurements and blood draws. ECG should be taken within 45 minutes prior to the methylprednisolone administration in all patients and within 60 minutes after completion of the ocrelizumab infusion (see Section 4.5.11). Additional ECGs may be taken at the discretion of the treating investigator, as required during an unscheduled visit.
- bb Vital signs (i.e., pulse rate, systolic and diastolic blood pressure, respiration rate, and temperature). On infusion visits, the vital signs should be taken within 45 minutes prior to the methylprednisolone administration in all patients. In addition, vital signs should be obtained prior to ocrelizumab infusion, then every 15 (± 5) minutes for the first hour, then every 30 (± 10) minutes until 1 hour after the end of the infusion. On non-infusion days, the vital signs may be taken at any time during the visit. Additional vital signs may be taken at the discretion of the treating investigator and should be recorded on the corresponding unscheduled Vital Signs eCRF.
- cc PK samples (predose and postdose): On infusion visits, two serum samples will be collected, one 5–30 minutes prior to the methylprednisolone administration and the second one 30 (± 10) minutes following the completion of the infusion of ocrelizumab. At other timepoints (non-infusion visits), samples will be collected at any time during the visit.
- dd ADA: On infusion visits (except on Day 15, and on the optional infusion visit for split dose if applicable), a serum sample is collected 5–30 minutes prior to the methylprednisolone administration.
- ee All patients will receive prophylactic treatment with an antihistamine and methylprednisolone prior to any infusion of ocrelizumab. Methylprednisolone dose (slow IV infusion to be completed approximately 30 minutes before the start of each infusion): adjusted to weight for patients < 40 kg (2 mg/kg methylprednisolone) and for patients ≥ 40 kg (100 mg methylprednisolone). In the rare case, when the use of methylprednisolone is contraindicated for the patient, an equivalent dose of an alternative steroid should be used as premedication prior to the infusion of ocrelizumab. IV or oral antihistamine (e.g., diphenhydramine) will be administered 30–60 minutes prior to ocrelizumab. The addition of an analgesic/antipyretic, such as acetaminophen/paracetamol, may also be considered.

Α	p	pendix	1:	Schedule of	f Activities
---	---	--------	----	-------------	--------------

#### Delayed Dosing Visit d Optional Ocrelizumab Extension (264 Weeks)a Φ WD from Trtmt Visit 9 Unsched. Site/MNf Opt Inf Visit for SD d. 29 31 32 34 35 37 38 40 41 Site or optional MN 30 33 36 39 visit b (MN) (MN) (MN) (MN) (MN) (MN) (MN) (MN) (MN) 190 c 192 204 214 c 216 228 238 c 240 252 262 ° 264 276 288 c Week 1331 1345 1429 1499 1513 1597 1667 1681 1765 1835 1849 1933 2017 Study day (± days) (± 6) (±6) (±6) (±6) (±6) (±6) (±6) (±6) (± 6) (±6) (±6) (±6) (±6) Telephone At Weeks 184, 188, 196, 200, 208, 212, 220, 224, 232, 236, 244, 248, 256, 260, 268, 272, 280, 284 (± 6 interview h days) SDMT Х х х Х Х (X) (X) х Visual testing (ETDRS and LCVA Х х х Х Х (X) (X) Х charts) i Physical Х х Х х х Х Х х х х х х Х х х х х examination j Weightk х х х х Х (X) х Height (X) х х х Х х Х Tanner staging m х (X) х Х Х Date of menarche х х (X) Х Х х Х х х х х х х х Х Wrist/Hand X-rayn х х Х (X) (X) ° Brain MRI scanp Х Х Х (X) Х х Neurological examination and (X) х х х х х Х Х EDSSq Concomitant Х Х Х Х Х Х Х Х Х х Х Х Х Х Х Х х medicationr Adverse events s Х Х Х Х х Х х Х Х Х Х Х Х Х х х Х Clinical relapses х х Х х х х х Х Х х х х х Х х х х Thyroid function х Х х Х Х (X) (X) Х testst

Ocrelizumab—F. Hoffmann-La Roche Ltd 141/Protocol WA39085, Version 10

#### Appendix 1: Schedule of Activities

				O	otional C	Crelizum	ab Exten	sion (26	4 Weeks	) a				lt d	e	÷	0
Site or optional MN visit b	29 (MN)	30	31 (MN)	32 (MN)	33	34 (MN)	35 (MN)	36	37 (MN)	38 (MN)	39	40 (MN)	41 (MN)	osing Visi	sit for SD	I. Site/MN	Trtmt Visit
Week	190 c	192	204	214 c	216	228	238 c	240	252	262 c	264	276	288 c	ed D	ľ <is< td="">chec	E O	</is<>	chec	E O
Study day (± days)	1331 (± 6)	1345 (± 6)	1429 (± 6)	1499 (± 6)	1513 (± 6)	1597 (± 6)	1667 (± 6)	1681 (± 6)	1765 (± 6)	1835 (± 6)	1849 (± 6)	1933 (± 6)	2017 (± 6)	Delay	Opt In	Unso	WD fr
Hepatitis B ∨irus DNA u	(X)			(X)			(X)			(X)			(x)			(x)	(x)
Total Ig, IgA, IgG, and IgM	x			x			x			x			x	(x)		(x)	
Immunologic assessments (including CD4%) v	x		x	x		x	x		x	x		x	x	(X)		(X)	x
Routine safety laboratory w	x	(x)	x	(X)	(x)		(X)	x									
Pregnancy test x	X	x	x	X	X	х	x	x	х	X	x	х	х	Х	X	(X)	x
Antibody titers y		x			x			x			x		x	(X)		(X)	x
Plasma/Urine banking for JCV z		x			x			x			x		x	(x)		(x)	x
Serum biomarker aa		Х						х					х				(X)
Optional RBR DNA bb		x															
Review of re-treatment criteria c		x			x			x			x			x	x		
Twelve-lead ECG (predose and postdose) cc		x			x			x			x			x	x	x	x
Vital signs dd	x	x	x	x	x	x	x	x	х	x	x	x	x	x	x	x	x

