# 2. OBJECTIVES AND ENDPOINTS

This *8*-year study will evaluate the safety, tolerability, pharmacokinetics, and PD effects of ocrelizumab in children and adolescents ages  $\geq$  10 to < 18 years with RRMS. The data from this study will serve to determine the dosing regimen of ocrelizumab to be further investigated in the subsequent Phase III study in children and adolescents. In addition, new emergent data (e.g., Real World Evidence data) may be used to support the dose selection. Specific objectives and corresponding endpoints for the study are outlined below.

Primary Pharmacokinetic Objective	Corresponding Endpoint
To characterize the ocrelizumab PK profile in children and adolescents	Serum concentration of ocrelizumab at specified timepoints
Primary Pharmacodynamic Objective	Corresponding Endpoint
To evaluate relationship between drug exposure and PD (CD19+ B-cell	Levels of CD19+ B-cell count in blood
count) in children and adolescents	
Secondary Safety Objective	Corresponding Endpoints
To evaluate safety of ocrelizumab in children and adolescents	Occurrence and severity of adverse events, with severity determined according to NCI CTCAE v5.0
	Change from baseline in vital signs
	Change from baseline in clinical laboratory test results
	• Level of circulating B cells, T cells, natural killer cells, and other leukocytes
	• Developmental milestones (e.g., growth, bone age, age at menarche, Tanner staging)
	
 
Non–MS CNS pathology as measured by brain MRI scans
 

	
 
Levels of blood immunoglobulins
 

	
 
Antibody titers against standard vaccines
 

Secondary Immunogenicity Objective	Corresponding Endpoint
To assess ADA development to ocrelizumab	• Presence of ADAs during the study relative to the presence of ADAs at baseline
Exploratory Objective	Corresponding Endpoints
To evaluate exploratory parameters	
 
Nature, frequency, and severity of clinical and protocol–defined relapses
 

	Change in EDSS
	Change in total number of new and/or enlarging T2     hyperintense lesions
	Total number of T1 gadolinium–enhancing lesions at Week 12
	Change in Symbol Digit Modalities Test
	Change in low-contrast visual acuity

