# 4.5.3.6 Withdrawal Visit

At the moment a patient meets one or more of the withdrawal criteria, or if a patient does not want to continue in the OOE period, this patient is regarded as withdrawn from treatment. Patients who withdraw from ocrelizumab treatment must complete all assessments (i.e., withdrawal visit) as shown in the schedule of activities (see Appendix 1) and will enter the SFU period.

It is important to distinguish between "withdrawal from treatment" and "withdrawal from study." Patients who withdraw from treatment should be encouraged to remain in the study for the full duration of the SFU period (104 weeks following the last infusion).

Despite all efforts, patients who withdraw from the study before entering the SFU period or during the SFU period should undergo the assessments shown in the schedule of activities.

At the withdrawal visit, an MRI scan will be required only if one was not performed in the previous 4 weeks. Thereafter, it is at the discretion of the treating investigator to decide on further treatment of the underlying disease. However, since sufficient data are not available to inform risks associated with switching to other products, the following recommendations are given:

- Caution is advised while patients remain B-cell depleted.
- Because of the unknown safety risk of administering DMTs for MS after discontinuation of ocrelizumab, certain treatments for MS such as lymphocytedepleting agents or lymphocyte-trafficking blockers (e.g., alemtuzumab, natalizumab, fingolimod, dimethyl fumarate, cyclophosphamide, azathioprine) are strongly discouraged for as long as the patient remains B cell depleted because of unknown effects on the immune system (e.g., increased risk, incidence, or severity of infection).

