## 5.1.1.4 Decrease in Immunoglobulins

Treatment with ocrelizumab resulted in a decrease in total Igs over the controlled period of the studies, mainly driven by reduction in IgM. The proportion of patients with decrease in Igs below LLN increased over time and with successive dosing. Based on additional patient exposure, in cases of continuous decrease over time, a high risk of serious infection cannot be ruled out (see Section 5.1.1.5).

Patients with IgG and IgM below the exclusionary levels per Section 4.1.2.3 at screening will not be enrolled in the study. The investigator should closely monitor the patient's IgG and IgM levels during the study. If their levels decrease below the exclusionary levels following ocrelizumab treatment and require specific medical care or management, repeat dosing may be suspended until resolved or held indefinitely as per the judgement of the treating investigator.

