#### 5.1.1.5 Serious Infections Related to Decrease in Immunoglobulins (Particularly in Patients Previously Exposed to Immunosuppressive or Immunomodulatory Drugs or with Preexisting Hypogammaglobulinemia)

Based on additional patient exposure, an association between decrease in Igs and serious infections with ocrelizumab treatment was observed and was most apparent for IgG. There was no difference in the pattern (type, latency, duration, outcome) of the serious infections reported in this subset of patients compared to the overall serious infections profile. In addition, risk factors for a subset of patients at higher risk of serious infections could not be identified.

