e Administration of IV ocrelizumab: The first dose of ocrelizumab must be administered as two infusions of half the dose 14 days apart (e.g., 150 mg on Day 1 and 150 mg on Day 15 for the 300 mg ocrelizumab cohort). It is recommended to schedule the first infusion of ocrelizumab (Day 1 of Dose 1) in the morning to allow the patient to stay at the hospital (or infusion center) with medical supervision and monitoring as required, as long as possible (e.g., until 6 p.m. or 8 p.m. according to the hospital rules), with a minimum of 1 hour after completion of the infusion. Patients may be hospitalized for a 24-hour observation after completion of the infusions in the discretion of the treating investigator. It is also recommended to administer the second infusion (Day 15 of Dose 1) and subsequent infusions in the morning, as patients should remain under observation for at least 1 hour after the completion of the infusion and up to 24 hours at the treating investigator's discretion.

For patients continuing in the optional ocrelizumab extension period (footnote a), subsequent doses will be administered as single infusions (e.g., 300 mg for the 300-mg ocrelizumab cohort). However, whenever the subsequent dose is higher than the previous dose, it should be administered as two infusions of half the dose 14 days apart. In this case, the second infusion will take place as an optional infusion visit for split dose. Prior to subsequent infusion of ocrelizumab, the treating investigator must review the clinical and laboratory re-treatment criteria (footnote c). Patients and their parents/legal guardian will be advised that an IRR can occur until 24 hours after completion of each infusion. A telephone interview will be conducted by site personnel within  $24 (\pm 4)$  hours after completion of each infusion (footnote h).

- f Unscheduled site or MN visit: Assessments performed at unscheduled (non-dosing) visits will depend on the clinical needs of the patient. All patients with new neurological symptoms suggestive of relapse should have EDSS performed within 7 days of the onset of the relapse. Other tests/assessments may be done as appropriate.
- g Withdrawal from treatment visit only takes place if patient discontinues prematurely from treatment (i.e., before Week 288) (see Section 4.5.3.6).

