- Routine safety laboratory (hematology, chemistry, and urinalysis): On infusion visits, all urine and blood samples should be collected prior to the methylprednisolone administration. At other times, samples will be collected at any time during the visit. For urinalysis, a urine dipstick for blood, protein, nitrite and glucose (using the dipsticks provided) will be performed. If abnormal and applicable a microscopic examination will be performed on site (local laboratory). For more information related to safety laboratory assessments, see Section 4.5.19.1.

- × Serum  $\beta$ -hCG must be performed at screening in female patients of childbearing potential (e.g., in Tanner stages  $\geq$  2 or post-onset of menarche). Subsequently, urine  $\beta$ -hCG (sensitivity of at least 25 mIU/mL) will be performed. On infusion visits, the urine pregnancy test should be performed prior to the methylprednisolone administration in all female patients of childbearing potential. If positive, the patient will not receive the scheduled dose, and confirmation by a serum pregnancy test will be performed.
- y Antibody titers: Measurement of antibody titers against common antigens (mumps, rubella, varicella zoster, and S. pneumoniae) will be performed.
- z Plasma and urine samples for JCV will be collected at specified timepoints and analyzed in batches, if decided by the Sponsor.
- aa Blood to be drawn for serum prior to dosing at the indicated timepoints. A single serum sample will be collected if patients withdraw from treatment prior to Week 192 (at the withdrawal from treatment visit).
- bb A single RBR DNA blood sample to be collected for research purposes if patient and/or parents/legal guardian agrees to separate optional RBR consent. This collection can be drawn at any subsequent visit if missed.
- cc ECG (predose and postdose): At screening, ECG may be taken at any time during the visit. On infusion visits, ECGs should be performed prior to receipt of study drug, prior to vital sign measurements and blood draws. ECG should be taken within 45 minutes prior to the methylprednisolone administration in all patients and within 60 minutes after completion of the ocrelizumab infusion (see Section 4.5.11). Additional ECGs may be taken at the discretion of the treating investigator, as required during an unscheduled visit.

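### Table 2b does not require immunoglobulins at the withdrawal-from-treatment visit, although Tables 1 and 2a do, so late premature withdrawals can go about 49 weeks between scheduled values

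*Combined protocol and SAP*

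**What the plan says.** - **Endpoint.** Section 2, Table 1 lists "Levels of blood immunoglobulins" among the secondary safety endpoints.
- **Schedules.** In Appendix 1, the row "Total Ig, IgA, IgG, and IgM" carries a required mark in the withdrawal column of Tables 1 and 2a. In Table 2b the row has required marks at Weeks 190, 214, 238, 262 and 288 and optional marks at delayed-dosing and unscheduled visits. Its withdrawal cell is empty.
- **Which visit.** Footnote g of Table 2b reads "Withdrawal from treatment visit only takes place if patient discontinues prematurely from treatment (i.e., before Week 288", so the visit applies only to premature discontinuers.
- **What is done there.** Section 4.5.3.6 defers to the table: "Patients who withdraw from ocrelizumab treatment must complete all assessments (i.e., withdrawal visit) as shown in the schedule of activities".
- **Risk.** Section 5.1.1.4 states: "The proportion of patients with decrease in Igs below LLN increased over time and with successive dosing". Section 5.1.1.5 adds that, with further exposure, "an association between decrease in Igs and serious infections with ocrelizumab treatment was observed and was most apparent for IgG".
- **After withdrawal.** Appendix 1, Table 3 has no Ig at SFU Week 12. The first is at SFU Week 24, counted from the withdrawal visit.

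**The concern.** The same visit has different content depending on when the patient leaves, and the missing item is the laboratory measure of an identified risk. The blank does not look deliberate. Ig stays scheduled to the end of treatment, so it was not phased out, unlike pre-dose PK sampling, which Section 4.5.19.6 ends at Week 96 of the extension. No footnote or section gives a reason.

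The affected patients are those with the longest exposure among premature discontinuers. Some may be leaving because of infection, since Section 4.6.1 makes a Grade 4 infection a reason for permanent discontinuation. A value at withdrawal would show the Ig level close to that event and give the starting point for judging recovery in follow-up. With a maximum of approximately 36 patients enrolled, few can supply such values.

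**Working it through.** The plan states no figure to reproduce. The check compares the rows and then counts weeks at nominal visit times, ignoring visit windows.

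**1. Withdrawal cell of the Ig row**

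| Appendix 1 table | Scheduled Ig draws | Withdrawal cell |
|---|---|---|
| Table 1 | Screening, Day 1, Weeks 12, 22 (Week 24 if not done at 22) | required |
| Table 2a | Weeks 46, 70, 94, 118, 142, 166 | required |
| Table 2b | Weeks 190, 214, 238, 262, 288 | blank |

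The Table 2b row has 17 cells for 17 columns (13 visits plus delayed dosing, split-dose infusion, unscheduled and withdrawal), so the blank falls in the withdrawal column. Neighbouring rows, such as "Immunologic assessments (including CD4" percentage), antibody titers, JCV banking and vital signs, are marked there.

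**2. Whether another row supplies Ig.** It does not. Footnote w defines its row as "Routine safety laboratory (hematology, chemistry, and urinalysis"). The immunologic row covers B-cell subsets, T cells and natural killer cells. Marks in parentheses are defined as optional.

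**3. Doses by the time of withdrawal.** Planned doses fall at Week 0 (Dose 1, split over Days 1 and 15) and every 24 weeks after that.
- By Week 190, the last dose is at Week 168: 168/24 + 1 = 8 doses.
- After Week 264: 264/24 + 1 = 12 doses.

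**4. Gap between scheduled values.**
Gap = (withdrawal week − last scheduled Ig week) + 24 weeks to SFU Week 24.
- Withdrawal at the Week 192 dosing visit, last Ig at Week 190: 2 + 24 = 26 weeks.
- Withdrawal at Week 213, last Ig at Week 190: 23 + 24 = 47 weeks.
- Withdrawal at Week 287, last Ig at Week 262: 25 + 24 = 49 weeks. This is the largest in whole weeks.

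Withdrawal in Weeks 181 to 189 falls between the labelled ranges of Tables 2a and 2b. The last draw is then at Week 166, at most 189 − 166 = 23 weeks earlier, so the maximum does not change.

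**5. With the cell marked.** There is a value at withdrawal and the next comes 24 weeks later. The worst case of 49 weeks is split into 25 and 24.

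**The case against.** **Other routes to a value exist, and this stands.** Section 4.5.19 permits unscheduled safety laboratory tests at any time. Section 5.1.1.4 asks investigators to monitor IgG and IgM closely. Section 4.5.3.3 has patients with signs of infection seen promptly, and Table 2b offers Ig as optional at unscheduled visits. A reader might infer that late discontinuers get no Ig value at all; the documents support only that none is required at this visit.

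**A recent on-treatment value usually exists, and this also stands.** Ig is drawn two weeks before each dose in the window, and Section 4.3.6 requires an IgG check before re-treatment. It would be wrong to say that the last on-treatment value is missing. A patient who stops at a failed pre-dose check has an Ig value about two weeks old.

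**The dose trend can be over-read.** It is tempting to say that low Ig is most frequent after 8 to 12 doses. Section 1.2.4.2 describes the trend in adult controlled periods of 96 and 120 weeks, so that is an inference. The protocol reports an association with serious infection but does not say that this grows with doses. For the controlled RMS studies it reports no association between sustained Ig decrease and infection rates.

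**The cell might have been lost in reproduction.** The routine safety laboratory row of Table 2b is visibly collapsed in the copy reviewed, so it cannot serve as a comparator. The Ig row is complete and other rows keep their withdrawal mark, which makes a loss unlikely but does not exclude it.

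**The consequence is small.** All analyses are descriptive and none is specified on a withdrawal-visit Ig. That limits the weight of the point but does not explain why the tables differ.

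**Conclusion.** The inconsistency holds. Tables 1 and 2a require Ig at the withdrawal-from-treatment visit, Table 2b does not, and nothing in the text restores or explains it. It concerns only premature withdrawals in the Table 2b window; completers have the Week 288 value.

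For those patients the interval between scheduled values around withdrawal ranges from about 24 weeks (withdrawal right after a draw) to about 49 weeks. A reader might compute 50 weeks from Week 262 to Week 288 plus 24, but the withdrawal visit exists only before Week 288.

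The conclusion assumes that the blank cell is in the source table and that visits occur at nominal weeks. The documents give no expected number of late withdrawals, so the number of affected patients cannot be estimated. No primary endpoint is touched. The effect is on completeness of one secondary safety endpoint tied to an identified risk, which makes correction worthwhile.

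**What to change.** Check the withdrawal cell of the Ig row in Table 2b against the source table. If it is blank, mark total Ig, IgA, IgG and IgM as required (x), as in Tables 1 and 2a. If the omission was intended, give the reason in a footnote.

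The cost is one table mark and one additional panel per late premature withdrawal. Blood is already drawn at that visit for the immunologic assessments and antibody titers, so no extra visit or venipuncture is needed. No dose or treatment rule changes.
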